6.2.3.4. Cycle 2 and Subsequent Cycles (Post-HSCT), Day 1 (± 3 days)

The following activities will take place during these visits:

- Physical examination
- Vital sign determinations
- ECOG performance status evaluation
- Review of concomitant medications
- 12-lead ECG (triplicate)
- Pregnancy testing; women of childbearing potential must have a negative urine pregnancy test result before the start of study treatment and every 3 months during the treatment phase.
- Collection of samples obtained before dosing for clinical laboratory tests (hematology, chemistry, and urinalysis)
- Bone marrow assessment of response by local pathology is required on Day 1 of Cycle 4 and every 3 cycles subsequently, and as clinically indicated
- AE/SAE evaluation
- Review of returned study medication and assessment of compliance

6.2.4. Schedule of Activities and Assessments for Subjects Receiving Salvage Chemotherapy

6.2.4.1. Cycle 1, Day 1

The following activities will take place during this visit:

- Physical examination
- Vital sign determinations
- ECOG performance status evaluation
- 12-lead ECG (triplicate) before dosing for subjects receiving MEC and LoDAC (subjects receiving FLAG-IDA will have triplicate ECGs on Day 2 of each cycle, instead of Day 1)
- Collection of samples obtained before dosing for clinical laboratory tests (hematology, chemistry, and urinalysis)
- A urine pregnancy test must be performed prior to dosing and every 3 months during the treatment phase in women of child-bearing potential
- Review of concomitant medications

- AE/SAE evaluation
- If consent is provided, collection of samples (blood [Pax gene DNA, Pax gene RNA, and PBMC] and buccal swab) obtained before dosing for pharmacogenomic and proteomic determinations
- Administration of MEC or FLAG-IDA at the study site.
Note: Additional study site visits are required for subjects receiving MEC (Days 1 through 5) or FLAG-IDA (Days 1 through 6). MEC and FLAG-IDA are administered for up to 2 cycles.
- LoDAC should be administered for 10 days in a 28-day cycle in the clinic unless arrangements can be made for administration outside of the clinic. If dosed outside the clinic a review of medication returned and assessment of compliance must be conducted at the beginning of each cycle.

6.2.4.2. Cycle 1, Day 2 and Day 8 (±1 day)

The following activities will take place during these visits:

- Physical examination
- Vital sign determinations
- Review of concomitant medications
- 12-lead ECG (triplicate) before dosing for subjects receiving FLAG-IDA on Day 2. All chemotherapy subjects will have 12-lead ECGs (triplicate) on Day 8.
- Collection of samples obtained before dosing for clinical laboratory tests (hematology, chemistry, and urinalysis)
- AE/SAE evaluation
- Administration of MEC or FLAG-IDA at the study site.
Note: Additional study site visits are required for subjects receiving MEC (Days 1 through 5) or FLAG-IDA (Days 1 through 6). MEC and FLAG-IDA are administered for up to 2 cycles.
- LoDAC should be administered for 10 days in a 28-day cycle in the clinic unless arrangements can be made for administration outside of the clinic. If dosed outside the clinic a review of medication returned and assessment of compliance must be conducted at the beginning of each cycle.

6.2.4.3. Cycle 1, Day 15 (±1 day)

The following activities will take place during this visit:

- Physical examination
- Vital sign determinations
- ECOG performance status evaluation
- Review of concomitant medications

- 12-lead ECG (triplicate) before dosing
- Collection of samples obtained before dosing for clinical laboratory tests (hematology, chemistry, and urinalysis)
- AE/SAE evaluation

6.2.4.4. Cycle 1, Day 29 (\pm 14 days)

- Bone marrow aspiration and biopsy for determination of response for high intensity chemotherapy (MEC or FLAG-IDA).

6.2.4.5. Cycle 2, Day 1 (\pm 3 days)

The following activities will take place during this visit:

- Physical examination
- Vital sign determinations
- ECOG performance status evaluation
- Review of concomitant medications
- 12-lead ECG (triplicate) before dosing for subjects receiving MEC and LoDAC (subjects receiving FLAG-IDA will have triplicate ECGs on Day 2 of each cycle, instead of Day 1)
- Collection of samples obtained before dosing for clinical laboratory tests (hematology, chemistry, and urinalysis)
- MUGA scans or ECHO to be performed in subjects receiving FLAG-IDA before dosing to determine eligibility for a second cycle
- AE/SAE evaluation
- Bone marrow aspiration and biopsy for determination of response for LoDAC. Bone marrow samples are also required Day 1 of Cycle 3. If a subject continues to receive LoDAC past Cycle 2, bone marrow assessments will be repeated on Day 1 of each subsequent cycle unless the subject has already achieved a CR, CRp, or CRi. In that event, bone marrow testing will be repeated after every 3 subsequent cycles, unless there is evidence of relapse.
- LoDAC should be administered for 10 days in a 28 day cycle in the clinic unless arrangements can be made for administration outside of the clinic. If dosed outside the clinic a review of medication returned and assessment of compliance must be conducted at the beginning of each cycle. Treatment with LoDAC may continue past Cycle 2. Subsequent cycles will follow same procedures as Cycle 2.
- Administration of MEC or FLAG-IDA at the study site.
Note: Additional study site visits are required for subjects receiving MEC (Days 1 through 5) or FLAG-IDA (Days 1 through 6). MEC and FLAG-IDA are administered for up to 2 cycles.

6.2.4.6. Cycle 2, Day 15 (± 3 days)

The following activities will take place during this visit:

- Physical examination
- Vital sign determinations
- ECOG performance status evaluation
- Review of concomitant medications
- 12-lead ECG (triplicate) before dosing
- Collection of samples obtained before dosing for clinical laboratory tests (hematology, chemistry, and urinalysis)
- AE/SAE evaluation

6.2.5. Schedule of Activities and Assessments after Treatment

6.2.5.1. End of Treatment Visit

The end of treatment visit should occur within 7 days of the last dose of quizartinib or correspond to Day 29 for the last cycle of salvage chemotherapy. For MEC or FLAG-IDA the end of treatment visit would be Cycle 1 Day 29 or Cycle 2 Day 29.

For subjects on quizartinib who discontinue treatment with the objective of proceeding to HSCT, a quizartinib end of treatment visit should occur. Additionally subjects moving onto HSCT must have a 30 Day Follow-up phone contact. Subsequently, if subject undergoes HSCT, restarts quizartinib and later discontinues treatment, a post-HSCT end of treatment visit should also occur.

The following activities will take place during this visit:

- Physical examination
- Vital sign determinations
- ECOG performance status evaluation
- Review of concomitant medications
- Serum pregnancy testing for women of childbearing potential
- 12-lead ECG (triplicate)
- Collection of samples for clinical laboratory tests (hematology, chemistry, and urinalysis)
- Bone marrow aspiration and biopsy for local response determination are preferred, but biopsy may be omitted if the aspirate is considered to be adequate. For subjects receiving chemotherapy response assessment may be at Day 29 \pm 14 days.
- Collection of specimen for exploratory assessment of FLT3 mutations using bone marrow or whole blood will be performed (for subjects in the quizartinib arm only).

- If consent is provided, collection of blood (Pax gene RNA) for pharmacogenomic and proteomic determinations
- AE/SAE evaluation
- Review medication and assessment of compliance

Note: Physical examination, vital sign determinations, ECOG performance status determination, and clinical laboratory tests need not be repeated if they were performed at a regularly scheduled visit within 3 days of the end of treatment visit.

6.2.5.2. Cross-Over Procedures

In the event that the study outcome demonstrates a clinical benefit to subjects on the quizartinib arm, subjects who were randomized to salvage chemotherapy may be eligible to cross-over to treatment with quizartinib.

Eligible subjects will be screened as outlined below before a subject can cross-over to quizartinib. Unless otherwise specified, screening procedures can be completed within 3 days of the end of treatment visit to determine that subjects meet inclusion criteria and do not meet exclusion criteria.

- Written informed consent
- Physical examination
- Vital sign determinations
- ECOG performance status evaluation
- Assessment of prior and concomitant medications
- Determination of coagulation profile (PT/INR)
- 12-lead triplicate electrocardiogram (ECG)
- Collection of samples for clinical laboratory tests (hematology and chemistry)
- AE/SAE evaluation
- Determination of survival and subsequent antileukemic treatments and their outcomes

Note: Clinical laboratory tests need not be repeated if they were performed within 3 days at the End of Treatment visit, and 3 days prior to the start of quizartinib treatment. There is no washout period required between stopping salvage chemotherapy and starting treatment with quizartinib.

6.2.5.3. 30-Day Follow-Up

The following activities will take place during this visit for subjects on quizartinib or salvage chemotherapy.

For subjects who discontinue quizartinib with the objective of proceeding to HSCT, a quizartinib 30-Day Follow-up visit should occur. Additionally these subjects will be followed in long-term follow-up until they resume quizartinib dosing. Subsequently, if subject undergoes HSCT, takes quizartinib and ends treatment, a post-HSCT 30-Day Follow-up visit should also occur.

For subjects who discontinue salvage chemotherapy and do not qualify for cross-over to quizartinib treatment, a 30-Day Follow-up visit should occur. Additionally these subjects will be followed in Long-Term Follow-up.

Telephone contact with the subject is sufficient unless any assessment must be repeated for resolution of treatment-related AEs:

- AE evaluation; SAE information will be collected at a minimum of 7 days after the end of treatment visit if the subject undergoes HSCT.
- Determination of survival and subsequent antileukemic treatments and their outcomes
- Review of concomitant medications used up to 30-Day Follow-up

6.2.5.4. Long-Term Follow-Up

The following activities will take place during Long-Term Follow-up:

- Determination of survival and subsequent antileukemic treatments and their outcomes, evaluated by telephone contact every 3 months
 - Subjects who stopped quizartinib to move onto HSCT will be followed until they resume quizartinib dosing
- If direct contacts are not possible due to withdrawal of consent or the subject becomes lost to follow-up, the site must make every effort to collect survival status from public records (eg, death certificates) in accordance with local laws. See Section 5.4.4 for further details on how subjects will be followed for vital status if they withdraw consent.

6.2.6. Early Termination/End of Study

Every effort should be made to continue to follow subjects after treatment discontinuation including if treatment is declined by the subject. If the subject declines study treatment before receiving any treatment, the reason for declining treatment, and information on any additional AML therapy should be collected. Subjects should continue to be followed at 3 monthly intervals for additional treatment, remission status and survival information.

Subjects withdrawn from the study and study follow up, or who withdraw consent after receiving at least 1 study drug dose should return to the study site for the early termination/end of study visit within 7 days (± 1 day) of the withdrawal decision. The following activities will take place during this visit:

- Review of concomitant medications
- AE/SAE assessment
- Review of returned study medication and assessment of compliance, for subjects receiving quizartinib or LoDAC

Every effort must be made to contact the subject and have him or her return to the study site for the early termination/end of study visit. If the subject cannot return to the site, the reason for and date of termination of the subject's participation in the study must be recorded on the appropriate CRF. If the subject is withdrawn or withdraws consent more than 30 days after study treatment

discontinuation, telephone contact is sufficient and if possible, reason for withdrawal, remission status, and information on any additional AML therapy should be collected.

7. EFFICACY EVALUATION

Primary Efficacy Variable

The primary efficacy variable is overall survival, defined as the time from randomization until death from any cause. Subjects alive or lost to follow-up at the time of analysis will be censored at the date when they were last known to be alive.

Secondary Efficacy Variable

The secondary variable is EFS, defined as the time from randomization until documented refractory disease, relapse after CRc, or death from any cause, whichever is observed first. Subjects alive without treatment failure or relapse or lost to follow-up at the time of analysis will be censored at the date of their last response assessment.

Additional Efficacy Variables

- Leukemia-free survival is the time from the first documented response (CR, CRp, or CRi) until documented relapse or death from any cause. Subjects alive without relapse or lost to follow-up at the time of analysis will be censored at the date of their last response assessment.
- Composite complete remission (CRc) rate is the percent of subjects achieving a best response of CR, CRp, or CRi.
- Complete remission (CR) rate is the percent of subjects achieving CR.
- Duration of CRc is the time from the first documented CRc (CR + CRp + CRi) until documented relapse. Subjects alive without relapse, lost to follow-up, or who have died without report of relapse as of the time of analysis will be censored at the date of their last response assessment.
- Duration of CR is the time from the first documented CR until documented relapse. Subjects alive without relapse, lost to follow-up, or who have died without report of relapse as of the time of analysis will be censored at the date of their last response assessment.
- Transplantation rate (bridge to transplant) is the percent of subjects undergoing HSCT directly following protocol specified treatment with no intervening AML therapy.

7.1. Method of Assessment

Bone marrow aspiration and biopsy for morphology are preferred, but biopsy may be omitted if the aspirate is considered to be adequate.

For subjects receiving quizartinib, bone marrow samples are required during Screening (within 14 days prior to the first dose of study drug), Cycle 2 Day 1, Cycle 3 Day 1, at the end of treatment study visit, and as clinically indicated. If the subject has already achieved a CR, CRp, or CRi, bone marrow testing will be repeated after every 3 subsequent cycles. A central laboratory will review the screening specimen to confirm the diagnosis.

For subjects receiving salvage chemotherapy, bone marrow samples are required at screening (within 14 days prior to the first dose of chemotherapy), on Day 29 ± 14 days of Cycle 1, on Day 29 ± 14 days Cycle 2, or as clinically indicated. If a subject continues to receive LoDAC past Cycle 2, bone marrow assessments will be repeated on Day 1 of each subsequent cycle unless the subject has already achieved a CR, CRp, or CRi. In that event, bone marrow testing will be repeated after every 3 subsequent cycles.

7.2. Response Definitions

Response to treatment will be defined per modified Cheson criteria¹⁸ as outlined below.

7.2.1. Complete Remission (CR)

For subjects to be classified as being in CR, they must have bone marrow regenerating normal hematopoietic cells and achieve a morphologic leukemia-free state (<5% bone marrow blasts in bone marrow, no blasts with Auer rods and no persistence of extramedullary disease) and must have an ANC >1 × 10⁹/L and platelet count ≥100 × 10⁹/L and they will be RBC and platelet transfusion independent (defined as 4 weeks without RBC transfusions and 1 week without platelet transfusion).

7.2.2. Complete Remission with Incomplete Platelet Recovery (CRp)

For subjects to be classified as being in CRp, they must achieve CR except for incomplete platelet recovery (<100 × 10⁹/L).

7.2.3. Complete Remission with Incomplete Hematological Recovery (CRi)

For subjects to be classified as being in CRi, they must fulfill all the criteria for CR except for incomplete hematological recovery with residual neutropenia <1 × 10⁹/L and/or platelet count <100 × 10⁹/L. RBC and platelet transfusion independence is not required.

7.2.4. Partial Remission

For subjects to be classified as being in PR, they must meet the criteria for CRi but only require a decrease of at least 50% in the percentage of blasts in the bone marrow with the total marrow blasts between 5% and 25% inclusive.

7.2.5. Relapse

Relapse after CR, CRp, or CRi is defined as a reappearance of leukemic blasts in the peripheral blood or $\geq 5\%$ blasts in the bone marrow aspirate or biopsy not attributable to any other cause or reappearance or new appearance of extramedullary leukemia.

Relapse after PR is similarly defined with reappearance of significant numbers of peripheral blasts and an increase in the percentage of blasts in the bone marrow aspirate to $>25\%$ not attributable to any other cause or reappearance or new appearance of extramedullary leukemia.

7.2.6. Best Response

Best response is defined as the best measured response (CR, CRp, CRi, PR, NR or Unknown) at any time post protocol specified treatment. Response will be assessed by the Investigator and derived per the modified Cheson criteria.

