5.6.4.5. Quizartinib Dose Interruption for HSCT

If a subject undergoes HSCT, quizartinib should be discontinued 7 days before the start of a conditioning regimen. For subjects randomized to the quizartinib arm who undergo HSCT, treatment with quizartinib may be resumed at 30 to 100 days after the transplant. A window of +7 days will be allowed after day 100. Quizartinib may be restarted if:

- Subject has an ANC $>1 \times 10^9/L$ and platelet count $>50 \times 10^9/L$ without platelet transfusion support within 1 week, or a platelet count $>25 \times 10^9/L$ without platelet transfusion support within 2 weeks prior to first dose.
- Subject does not have (1) active acute, or \geq Grade 3 graft versus host disease (GVHD) or (2) active GVHD therapy (not prophylaxis) initiation within 21 days.

The starting dose of quizartinib post-HSCT should be 30 mg daily unless the subject is receiving a strong CYP3A4 inhibitor, in which case the starting dose should be 20 mg daily. Subjects will dose escalate starting on Day 16 if the QTcF interval is less or equal to 450 msec prior to or at the day 15 ECG evaluations.

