^b Triplicate ECGs to be obtained on Day 1 of Cycle 1 post-HSCT before dosing, 2, and 4 hours after dosing; on Day 8 of Cycle 1 post-HSCT; Day 15 of Cycle 1 before dosing (including a determination of whether dose escalation is appropriate); Day 1 of Cycle 2 post-HSCT and all subsequent cycles. Following dose escalation, triplicate ECG determinations should be performed at least once weekly for 2 weeks to monitor QTcF prolongation.

^c Women of childbearing potential must have a negative urine pregnancy test before the start of study treatment and every 3 months during the treatment phase.

^d Bone marrow aspiration and biopsy for morphology determination are preferred, but biopsy may be omitted if the aspirate is considered to be adequate. Bone marrow samples are required on Day 1 of Cycle 1 post-HSCT (may be taken within 14 days prior to the first dose of study drug; this window may be extended after consultation with the Medical Monitor), on Day 1 of Cycle 4 and every 3 cycles subsequently, at the early termination/end of study visit, and as clinically indicated.

^e A bone marrow sample should be obtained at Day 1 Cycle 1 (may be taken with 14 days prior to dosing) for central determination of FLT3 mutations and mutations in other genes. FLT3 test result is not required to start quizartinib following transplantation.

^f Quizartinib should be taken in the morning.

Table 5 Schedule of Activities and Assessments for Subjects Receiving Salvage Chemotherapy

Activity	Screening (≤14 days from random- ization)	Cycle 1				Cycle 2	
		D 1	D 2 and D 8 ±1	D 15 ±3	D 29 ±14	D 1 ±3	D 15 ±3
Written informed consent	X						
Medical and disease history and demographics	X						
Physical examination	X	X	X	X		X	X
Vital sign determinations	X	X	X	X		X	X
ECOG performance status determination	X	X		X		X	X
Assessment of prior and concomitant medications	X ^a	X	X	X		X	X
Pregnancy test for women of childbearing potential	X ^b	X ^b					
Determination of coagulation profile (PT/INR)	X						
Chest X-rays (posterior/anterior and lateral)	X						
12-lead ECG (triplicate)	X ^c	X ^c	X ^c	X ^c		X ^c	X ^c
Clinical laboratory tests (hematology; chemistry; urinalysis)	X ^d	X ^d	X ^d	X ^d		X ^d	X ^d
MUGA scan or ECHO	X ^e					X ^e	
Bone marrow aspiration or biopsy	X ^f				X ^f		
Collection of bone marrow and whole blood specimen for central laboratory FLT3 mutation determination and other AML-associated mutations	X ^g						
AE/SAE assessment		X	X	X		X	X

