- ^g A bone marrow and peripheral blood sample should be obtained at screening (at approximately the same time) for determination of FLT3-ITD status. A bone marrow sample should be obtained at treatment discontinuation or relapse. The sample may also be tested for FLT3 point mutations and mutations in other AML-associated genes.
- ^h If consent is provided, blood sample (Pax gene DNA, Pax gene RNA, and PBMC) and buccal swab on Day 1 of Cycle 1 before dosing.
- ⁱ Additional study site visits are required for subjects receiving MEC (Days 1 through 5) or FLAG-IDA (Days 1 through 6). MEC and FLAG-IDA are administered for up to 2 cycles, depending on response and safety assessments.
- ^j Treatment with LoDAC may continue past Cycle 2 and subsequent cycles will follow same procedures as Cycle 2. . Low dose cytarabine should be administered for 10 days in a 28 day cycle in the clinic unless arrangements can be made for administration outside of the clinic. If dosed outside the clinic, a review of medication returned and assessment of compliance must be conducted at the beginning of each cycle.

Table 6 Schedule of Activities and Assessments After Treatment

Activity	End of Treatment Visit ^a	Cross-Over ^f	30-Day Follow-Up	Long-term Follow-Up	Early Termination / End of Study ^h
Written informed consent		X			
Physical examination	X ^b	X			
Vital sign determinations	X ^b	X			
ECOG performance status determination	X ^b	X			
Assessment of concomitant medications	X	X	X		X
Serum pregnancy test for women of childbearing potential	X				
Determination of coagulation profile (PT/INR)		X			
12-lead ECG (triplicate)	X	X			
Clinical laboratory tests (hematology; chemistry; urinalysis)	X ^b	X ^g			
Bone marrow aspiration or biopsy	X ^c				
Assessment of FLT3 mutations using bone marrow	X ^d				
Collection of blood for pharmacogenomic and proteomic determinations	X ^e				
AE/SAE assessment	X	X	X ^h		X
Review of returned study medication and assessment of compliance, for subjects receiving quizartinib or LoDAC	X				X ⁱ
Determination of remission status, subsequent antileukemic treatments and their outcomes, and survival		X	X ^h	X ⁱ	
Reason for withdrawal					X

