^a The end of treatment visit should occur within 7 days of the last dose of quizartinib. If quizartinib is discontinued a form must be completed so subject can proceed to HSCT. Additionally subjects moving onto HSCT must have the 30 Day Follow-up phone contact and will be evaluated in Long-Term Follow-up schedule until they resume quizartinib dosing. For subjects receiving chemotherapy the EOT visit corresponds to Day 29 of the last cycle. Assessment of best response to chemotherapy should be conducted at Day 29 (±14 days) or prior to starting subsequent AML therapy.

^b These assessments need not be repeated if they were performed at a regularly scheduled visit within 3 days of the end of treatment visit.

^c Bone marrow aspiration and biopsy to determine response status are preferred, but biopsy may be omitted if the aspirate is considered to be adequate. For subjects receiving chemotherapy the bone marrow and response assessment should be conducted at Day 29 ± 14 days.

^d FLT3 mutation analysis will be performed for subjects in the quizartinib arm only. A bone marrow sample (or peripheral blood sample if marrow cannot be obtained) should be obtained at the end of treatment for determination of FLT3-ITD status. The sample may also be tested for FLT3 point mutations and mutations in other AML-associated genes.

- ^e If consent is provided, collection of blood (Pax gene RNA) at end of treatment visit
- ^f Screening procedures can be completed within 3 days of the end of treatment visit to determine that subjects meet inclusion criteria and do not meet exclusion criteria. There is no washout period required between stopping salvage chemotherapy and starting treatment with quizartinib.
- ^g For the Cross-over period, only hematology and chemistry samples will be collected. Clinical laboratory tests need not be repeated if they were performed within 3 days at the End of Treatment visit, and 3 days prior to the start of quizartinib treatment.
- ^h Telephone contact with the subject is sufficient unless any assessment must be repeated for resolution of treatment-related AEs.
- ⁱ Early Termination/End of Study is for subjects withdrawing consent, discontinuing treatment and/or follow up. Review of returned medication is required for subjects receiving study drug at time of withdrawal.
- ^j Telephone contact every 3 months.

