6.2.3. Schedule of Activities and Assessments for Subjects Receiving Quizartinib After HSCT

6.2.3.1. Cycle 1 (Post-HSCT), Day 1

The following activities will take place during this visit:

- Physical examination
- Vital sign determinations
- ECOG performance status evaluation
- Review of concomitant medications
- 12-lead ECG (triplicate) before dosing and 2 and 4 hours after dosing

- Pregnancy testing; women of childbearing potential must have a negative urine pregnancy test result before the start of study treatment and every 3 months during the treatment phase.
- Collection of samples obtained before dosing for clinical laboratory tests (hematology, chemistry, and urinalysis) (blood draws may be performed the prior day; results should be reviewed before dosing)
- Bone marrow aspiration and biopsy for response determination; biopsy may be omitted if the aspirate is considered to be adequate
- Specimen collection for exploratory assessment of FLT3 mutations using bone marrow (or whole blood if marrow cannot be collected); result of FLT3 test not required for subject to start quizartinib.
- AE/SAE evaluation
- Administration of quizartinib at the study site

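### Best response has no stop at HSCT, and post-HSCT response marrows are scheduled only for quizartinib subjects who restart, so transplant remissions can raise the CR and CRc rates mainly in that arm

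*Combined protocol and SAP*

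**What the plan says.** **Definition.** Section 7.2.6: "Best response is defined as the best measured response (CR, CRp, CRi, PR, NR or Unknown) at any time post protocol specified treatment". Sections 5.7.3 and 7.6 build the CRc rate on best response. Section 5.7.3 does the same for the CR rate, and Section 7.7 gives that rate no time limit. Section 13.7 compares both rates between arms by CMH tests. Duration of CRc, duration of CR and LFS start at the first documented response (Sections 7.5, 7.8 and 7.9).

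**Quizartinib after HSCT.** Section 5.6.4.5 lets subjects randomized to quizartinib restart; treatment "may be resumed at 30 to 100 days after the transplant. A window of +7 days will be allowed after day 100". For those who do, Section 6.2.3.1 schedules "Bone marrow aspiration and biopsy for response determination" on post-HSCT Cycle 1 Day 1. Table 4, footnote d, places this marrow "on Day 1 of Cycle 1 post-HSCT (may be taken within 14 days prior to the first dose of study drug", and the window can be extended after consulting the Medical Monitor. Section 6.2.3.4 adds: "Bone marrow assessment of response by local pathology is required on Day 1 of Cycle 4 and every 3 cycles subsequently".

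**Chemotherapy.** Table 6, footnote a (and the synopsis under Follow-up): "Assessment of best response to chemotherapy should be conducted at Day 29 (±14 days) or prior to starting subsequent AML therapy". For LoDAC, Table 5, footnote f, and Section 6.2.4.5 schedule repeated marrows while treatment continues.

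**Follow-up without study drug, either arm.** Section 6.2.5.4: "Determination of survival and subsequent antileukemic treatments and their outcomes, evaluated by telephone contact every 3 months". Table 6 also lists "Determination of remission status, subsequent antileukemic treatments and their outcomes, and survival".

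**The concern.** A marrow remission after an allogeneic transplant reflects the conditioning and the graft as well as whatever came before. If such remissions count toward best response, both arms should have the same chance of having one recorded. Here the definition is common to both arms but the scheduled opportunity is not. A quizartinib subject who enters HSCT in PR or without response, and restarts, has a response marrow by schedule. A chemotherapy subject with the same course has telephone contact every 3 months.

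At stake are the between-arm comparisons of CR and CRc rates, and which subjects enter the duration and LFS analyses and when their clocks start. All of these are exploratory.

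**Working it through.** The plan gives no expected CR or CRc rate for this trial and no power for these comparisons, so there is no planned figure to reproduce. The check has two parts.

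**1. Timing of scheduled response marrows**

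- First post-HSCT marrow, quizartinib restarters: earliest 30 − 14 = day 16 after transplant; latest 100 + 7 = day 107. An extension by the Medical Monitor could make it earlier. A marrow taken before the first resumed dose cannot reflect resumed quizartinib.
- Post-HSCT Cycle 4 Day 1: 3 × 28 = 84 days after restart, so about day 30 + 84 = 114 to day 107 + 84 = 191 after transplant.
- MEC or FLAG-IDA: Day 29 ± 14, so Day 15 to Day 43 of each cycle.
- LoDAC: Day 1 of Cycles 2 and 3, then each cycle until remission, then every 3 cycles.
- Chemotherapy subjects after HSCT, and quizartinib subjects who do not restart: no scheduled response marrow.

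The imbalance is therefore confined to the period after HSCT.

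**2. Ceiling on the CRc rate in the quizartinib arm**

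Inputs: 242 subjects (Section 13.3); 35% bridged to HSCT (Section 5.2.5, from Phase 2); 94% of those proceeding to HSCT already in CRc or PR (Section 3.3, Phase 2); CRc and PR rates by dose (Table 1).

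- Transplanted: 0.35 × 242 = 84.7.
- In CRc or PR at HSCT: 0.94 × 84.7 = 79.6.
- In neither: 0.06 × 84.7 = 5.1, and 5.1/242 = 2.1 points.

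Only subjects not already in CRc can raise the CRc rate. Assume that PR makes up the same share of CRc + PR among transplanted subjects as in Table 1. Then the ceiling is 79.6 × PR/(CRc + PR) + 5.1:

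| Phase 2 dose | PR/(CRc + PR) | In PR at HSCT | Ceiling, subjects | Ceiling, points of 242 |
|---|---|---|---|---|
| 30 mg | 13/60 = 21.7% | 17.3 | 22.3 | 9.2 |
| 60 mg | 24/71 = 33.8% | 26.9 | 32.0 | 13.2 |
| 90 mg | 25/72 = 34.7% | 27.6 | 32.7 | 13.5 |
| 135 mg | 28/73 = 38.4% | 30.5 | 35.6 | 14.7 |
| 200 mg | 50/92 = 54.3% | 43.3 | 48.4 | 20.0 |

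This requires every such subject to restart and convert. The ceiling scales with the share restarting, which the documents do not give. As assumptions, 25% gives 2.3 to 5.0 points, 50% gives 4.6 to 10.0, and 75% gives 6.9 to 15.0. Each 10 upgraded subjects add 10/242 = 4.1 points.

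The CR rate has a larger pool, because subjects in CRp or CRi at HSCT could also move to CR. Table 1 does not split CRc, so that pool cannot be sized.

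**The case against.** **The text may already exclude these responses.** Section 13.4 treats transplantation as non-protocol AML therapy, and Section 7.10 distinguishes HSCT from protocol treatment. Read with these, a remission seen before restart can be excluded. That is reasonable but unstated, and it does not settle the marrows at Cycle 4 and later: resumed quizartinib is protocol treatment with its own response schedule. Two programmers could code the rule differently. Section 13.4 also refers to a statistical analysis plan for detail. No derivation text from such a plan was available, so the point is that the protocol does not state a rule, not that none exists.

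**Counting them may be intended.** Section 5.2.5 wants to evaluate quizartinib before HSCT and as maintenance. This supports reporting responses across the whole strategy. It does not support a between-arm test in which only one arm has scheduled marrows after transplant.

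**Chemotherapy is not limited to one early look.** This stands. LoDAC subjects have repeated marrows on treatment. Table 5 allows marrows when clinically indicated, and Table 6 collects remission status in follow-up for both arms. A reader might infer that a chemotherapy subject can never be credited with a post-HSCT remission. The documents do not say so, hence mainly and not only.

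**EFS.** A reader might infer that EFS is biased too, since it includes relapse after CRc. No such effect is shown. A subject without CRc before HSCT may already have had a refractory-disease event, and the direction of any remaining effect cannot be derived.

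**Conclusion.** The point holds and is minor. As written, transplant remissions can count toward best response, and the schedule gives quizartinib restarters the better chance of having one recorded. The exploratory CR and CRc rates can be raised mainly in that arm, and the clocks for duration and LFS can start at such a remission. The primary OS analysis is unaffected.

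The range of 9 to 20 points is a ceiling and should not be read as an estimate of inflation. It rests on Phase 2 bridging and response figures from a cohort with a different treatment history, on equal chances of transplant for CRc and PR subjects, and on every eligible subject restarting and converting. The upper end uses the 200 mg group, which had 12 subjects.

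**What to change.** In Section 7.2.6, for both arms, limit best response for the CR and CRc rates to assessments made before the start of HSCT conditioning or of any other non-protocol AML therapy. Use the same cut to identify the first CR or CRc for duration and LFS. The cut decides which responses count; it does not censor follow-up at HSCT. Report post-HSCT responses separately by arm, with the number of subjects who had a marrow, which preserves the aim in Section 5.2.5.

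Do not apply the cut to the relapse term in EFS: a subject first in CRc after HSCT who then relapses could lose that event.

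The cost is a few sentences and the matching derivation code. No new visits are needed, since Section 6.2.5.1 already provides an end-of-treatment visit with a response marrow for quizartinib subjects leaving treatment for HSCT. The quizartinib response rate may be slightly lower, and subjects whose first remission follows HSCT would leave the duration and LFS analyses. The sentences should be labelled as analysis rules; no treatment rule changes.
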